11.1 Stopping Rules

If we see no responses nor any evidence of disease stabilization (as defined above as stable disease ≥6mo) after the first 10 patients, then the trial will be halted for futility. If we see at least one response or capture at least one instance of disease

stabilization ≥6mo among the first 10 patients, then enrollment will continue to goal enrollment of 20 patients.

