this disease, MCL remains a largely incurable malignancy with a 3 year overall survival of 40-80% depending on age, gender and treatment regimen (i.e. chemoimunotherapy +/- ASCT) [3]. These data indicate that, despite improvements in therapeutic options for MCL, most patients will still relapse and eventually succumb to their malignancy. There exists, however, a subset of MCL patients that presents with an indolent form of the disease who are able to go months to years without MCL-directed therapy and whose long term prognosis is favorable. Defining patients with this indolent form of MCL at initial diagnosis is a clinical challenge and, thus far, there have been no clearly defined clinical or pathological features able to reproducible identify this subgroup; further prospective research is ongoing.

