- ⁵Research Labs include blood samples for serum hormone levels (DHT, DHEA, Androstenedione, Estrone). To be drawn at screening, after 4 weeks of treatment (+/- 6 days), after 12 weeks of treatment (+/- 6 days), and then every 12 weeks (+/- 6 days) during treatment. ⁶ May be obtained up to 8 weeks in advance of initiation of therapy (provided no additional anti-cancer therapies are administered during the interval). A Deauville score should be assigned.
- ⁷ At the beginning of therapy (within 3 days), then every four weeks for the first 12 weeks (+/- 6 days), then at a minimum of every 12 weeks (+/- 6 days) while on therapy, depending on clinical course. For the first day of therapy, pre-entry H&P, PS, disease assessment, and adverse event assessment may be used (these do not need to be repeated within 3 days) and labs done within 14 days are acceptable.
- ⁸ During treatment, restaging CT imaging will be performed every 12 weeks of therapy (+/- 7 days), or as indicated to evaluate clinical suspicion of disease progression. First restaging CT (three months after initiating therapy) should include PET imaging to ascertain metabolic response to therapy. Subsequently, restaging PET/CT should also be performed to confirm metabolic CR in patients with stable PR on 2 consecutive CT staging exams or in patients with a CR based on CT staging and baseline FDG-avid disease to determine metabolic CR and CR (resp.). A Deauville score should be assigned when restaging PET is performed.
- ⁹ Post therapy evaluation will be completed 30 days (+/-7 days) after the last dose of enzalutamide or prior to initiation of new therapy, whichever comes sooner.
- ¹⁰Long-term follow-up should be performed according to the patient's physician's standard of care. This may be performed at patients' local physician's offices. Long-term follow-up will assess survival and disease progression; subjects may be contacted by the study team until five years out from study completion, subject withdrawal of consent, lost to follow-up, or study termination by the investigator, whichever occurs first.
- ¹¹ When appropriate, archival tissue or fresh samples from clinical biopsies may be used.

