10.5 Progression-free Survival (PFS)

PFS will be measured as time from first study drug administration to the first occurrence of disease progression or death from any cause. Data for subjects without disease progression or death will be censored at the date of last disease assessment or date last known to be alive, respectively. The estimates will be formed using the all treated population. Progression-free survival will be calculated using assessments by investigators. Kaplan-Meier methodology will be used to estimate event-free curves and corresponding quartiles (including the median).

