10.6 Assessment Inadequate, Objective Status Unknown

Progression has not been documented and one or more target lesions or other sites of disease have not been assessed or inconsistent methods of assessment were used.

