11.2 Anticipated Accrual

We expect to accrue approximately 1 patient per month and anticipate complete study accrual in 24 months.

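### Does the futility rule in 11.1 need a named deciding scan and a written accrual hold?

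*Combined protocol and SAP*

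**What the plan says.** Section 11.1 (Stopping Rules) halts the trial on this condition: "If we see no responses nor any evidence of disease stabilization (as defined above as stable disease ≥6mo) after the first 10 patients". The other branch requires at least one response or one case of "stabilization ≥6mo among the first 10 patients, then enrollment will continue to goal enrollment of 20 patients".

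The imaging schedule is in Section 9.0 (Study Calendar), footnote 8: "During treatment, restaging CT imaging will be performed every 12 weeks of therapy (+/- 7 days"). The same footnote describes the week-12 scan this way: "First restaging CT (three months after initiating therapy) should include PET imaging to ascertain metabolic response to therapy".

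Section 11.2 gives the pace: "We expect to accrue approximately 1 patient per month and anticipate complete study accrual in 24 months".

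On the time origin, 10.5 says "PFS will be measured as time from first study drug administration". No other section gives a per-patient definition of six-month stable disease. Section 10.1.2 uses stable disease beyond 3 months for the disease control rate, and 11.0 uses a median PFS of at least 6 months, which describes a group.

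**The concern.** The rule exists to spare patients 11 to 20 if the first ten show no activity. Two omissions seem to weaken it.

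First, the deciding scan is open. The week-24 scan may fall anywhere from day 161 to day 175, and six calendar months is 182.6 days. Taken strictly, no scheduled week-24 scan can show six months, and week 36 would be the first that does. Two readers could then apply the rule 12 weeks apart. The reference to an earlier definition does not help, because there is none.

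Second, the hold is implied but not written. A site that kept enrolling while the first ten were followed would not plainly breach the text, and part of the protection would be lost.

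A third worry is patient mix. Section 2.1 describes patients with "an indolent form of the disease who are able to go months to years without MCL-directed therapy", and 5.1.2 admits untreated patients suited to watch and wait. One such patient could clear the rule without any drug effect.

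**Working it through.** **The plan's own figures.** The plan states no overrun. Its decision figures in 11.0 reproduce: the exact binomial probability of 4 or more responses in 20 is 0.133 at a true rate of 10% and 0.893 at 30% (stated as 0.13 and 0.89). Neither depends on when the look at ten patients takes place.

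**Inputs.** Scans every 84 days (9.0). Accrual of 1 per month, or 20/24 = 0.83 per month (11.2). One month = 30.4375 days. Week 12 is then 84/30.4375 = 2.76 months, week 24 is 5.52 months and week 36 is 8.28 months. The documents give no expected PFS, so I assume exponential PFS with medians of 1.5 to 4 months, one homogeneous population, no responses, and progression found at the next scheduled scan.

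**Ceiling without a hold, evenly spaced entry.** Enrolled = floor(10 + wait × rate).
- Week 24: floor(10 + 5.52) = 15 at 1 per month; floor(10 + 4.60) = 14 at 0.83.
- Week 36: floor(10 + 8.28) = 18; floor(10 + 6.90) = 16.

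**Average if the rule fires.** A stop needs all ten to have progressed, and many are resolved before the last scan. Patient 10 is resolved only at week 24 in 22% to 38% of week-24 stops. The stop comes at the latest documented progression.

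**How often it fires.** With F = 1 − 2^(−5.52/median), P(fire) = F^10. For a median of 2 months, F = 1 − 2^(−2.76) = 0.852 and 0.852^10 = 0.20. Overrun over all trials = P(fire) × mean extra.

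| Median PFS (months, assumed) | P(fire), week 24 | Mean extra if fired, 1/month | Mean extra if fired, 0.83/month | Mean extra over all trials, 1/month |
|---|---|---|---|---|
| 1.5 | 0.44 | 3.13 | 2.61 | 1.4 |
| 2 | 0.20 | 3.38 | 2.76 | 0.7 |
| 3 | 0.038 | 3.64 | 2.92 | 0.14 |
| 4 | 0.008 | 3.77 | 3.00 | 0.03 |

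On a week-36 reading, the last column becomes 3.2, 2.5, 1.1 and 0.4.

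**Random entry.** The ceiling of 4 to 5 extra holds only for even spacing. With Poisson entry, more than 5 extra patients enter in about 13% to 31% of week-24 stops.

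**Cost of a full hold.** At 1 per month, patient 10 enters at month 10 and the hold ends at 10 + 5.52 = 15.5. If patient 11 enters then, patient 20 enters at 15.5 + 9 = 24.5 months, or 25.5 if one more accrual interval passes first. Unheld accrual would end at month 20, so the 24 months in 11.2 absorb about 4 months. At 0.83 per month there is no slack, and accrual ends at about 28.3 to 29.5 months.

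**Chance of delaying a trial that then continues.** This is (1−q)^n − (1−q)^10, where q is the assumed chance that a patient qualifies and n is the number classified before patient 11 is due at month 11. For q = 0.05, 0.10 and 0.20, qualifying at week 12 (n = 8) gives 0.065, 0.082 and 0.060. Qualifying at week 24 (n = 5) gives 0.175, 0.242 and 0.220.

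**The case for a change.** The strongest case for a change is that the textual gaps depend on no model. The rule names no scan, cites a definition that does not exist, and leaves the hold to inference. This is the trial's only futility rule, and if it does fire without a hold, about a third of the ten patients it should protect have already entered. Firing is not remote in every scenario: if each patient has an assumed 10% chance of responding or staying stable for six months, it fires with probability 0.9^10 = 0.35. A patient whose assessment is inadequate under 10.6 ("one or more target lesions or other sites of disease have not been assessed or inconsistent methods of assessment were used") could also leave the ten unresolved.

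The textual observations stand, but they do not show that following the plan leads to a wrong decision. The faulty cross-reference is a clerical slip, because 11.1 states the six-month threshold itself, twice. Continuation is written as a consequence of seeing activity, so waiting is the ordinary reading. The week-36 reading needs calendar arithmetic that footnote 8 does not use. A patient with unknown status has not shown stabilization, and an analyst would count that patient so.

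The patient-mix point is separate. Indolent patients make a stop less likely whichever scan is used, so they reduce the expected overrun. Reporting how many of the first ten were watch-and-wait patients would be informative, but it would change no decision under the rule.

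**Conclusion.** No change to the plan follows. The natural reading of 11.1 with footnote 8 is that accrual waits after patient 10 and that the week-24 scan serves as six months. On that reading no extra patients are exposed. What remains is unwritten detail and a clerical slip in a pilot that 11.0 describes as not formally powered.

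If accrual did run on, a week-24 stop would come after about 2.6 to 3.8 extra patients on average. Over all trials, the overrun would be about 1.4 patients at a median PFS of 1.5 months, falling to 0.03 at 4 months (1 per month). Whether to pause is also a fair trade-off: a full hold costs up to about 5.5 months, and the chance of delaying a trial that then continues is about 0.06 to 0.24.

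These sizes rest on assumed exponential PFS, a homogeneous population, no responses and even entry. A strict week-36 reading or random entry would raise them. The conclusion on the text needs none of these assumptions.

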11.2 Anticipated Accrual

We expect to accrue approximately 1 patient per month and anticipate complete study accrual in 24 months.

11.3 Estimated Distribution of Study Population by Gender, Race and Ethnicity

Ethnic Category	Females	Males
American Indian/Alaska Native		
Asian	1	1
Native Hawaiian or Other Pacific Islander		
Black or African American	1	1
White	4	12
More than one race		
Unknown or not reported		
Racial Categories: Total of all subjects	6	14

12.0 STUDY MONITORING AND REPORTING PROCEDURES

12.1 Adverse Event (AE) Reporting

AEs of Grade 3 and above, and Serious Adverse Events (SAEs) occurring at any grade will be monitored and recorded in study-specific case report forms (CRFs) from the time of the first dose of study treatment through 30 days following the end of study treatment, or until the patient receives an alternative anti-cancer therapy, whichever date comes first. AEs related to lymph node (tumor) biopsies that are done solely for research study screening purposes will be monitored, recorded, and reported according to the same standards, with the exception that assessment of study drug attribution will be excluded from reporting criteria.

The Investigator will assess AE grading, attribution, expectedness and whether the event is of interest to Astellas/Medivation Inc.

The NCI Common Terminology Criteria for Adverse Events v4.0 (CTCAE) will be used to classify and grade toxicities.

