1.2 Secondary objectives

- 1.2.1 To evaluate the duration of disease control (progression free survival) in patients with MCL treated with enzalutamide.
- 1.2.2 To evaluate the safety profile of enzalutamide in MCL.
- 1.2.3 To gain preliminary data on clinical activity and toxicity of this regimen in male vs. female patients.

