3.0 DRUG INFORMATION

3.1 General Information

Enzalutamide (MDV3100) is an androgen receptor signaling inhibitor that targets several steps in the AR signaling pathway. Enzalutamide competitively inhibits binding of androgens to ARs, inhibits nuclear translocation of receptors and inhibits the association of the AR with DNA. Enzalutamide is currently FDA approved for the treatment of metastatic, castration-resistant prostate cancer (CRPC). As this medication has not previously been studied in patients with MCL, we will extrapolate dosing and adverse effect monitoring from clinical experience with enzalutamide in the setting of CRPC. Enzalutamide is sold and distributed by Astellas/Medivation, Inc. under the brand name XtandiTM.

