3.3.6 Laboratory Abnormalities

Grade 1-4 neutropenia occurred in 15% of patients on enzalutamide (1% Grade 3-4) and in 6% of patients on placebo (no Grade 3-4). The incidence of Grade 1-4 thrombocytopenia was similar in both arms; 0.5% of patients on enzalutamide and 1% on placebo experienced Grade 3-4 thrombocytopenia. Grade 1-4 elevations in ALT occurred in 10% of patients on enzalutamide (0.3% Grade 3-4) and 18% of patients on placebo (0.5% Grade 3-4). Grade 1-4 elevations in bilirubin occurred in 3% of patients on enzalutamide and 2% of patients on placebo.

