3.3.7 Hallucinations

1.6% of patients treated with enzalutamide were reported to have Grade 1 or 2 hallucinations compared to 0.3% of patients on placebo. Of the patients with hallucinations, the majority were on opioid containing medications at the time of the event. Hallucinations were visual, tactile, or undefined.

3.4 Pregnancy/Breast Feeding:

Enzalutamide is a pregnancy category X medication and is contraindicated in women who are pregnant or who are planning to become pregnant. A confirmed negative pregnancy test will be required for all female subjects prior to enrollment and both male and female subjects will be counseled on and required to employ effective use of barrier contraception from the start of therapy through a minimum

of 3 months after the last dose. Enzalutamide has not been studied in breast feeding mothers and its excretion characteristics in breast milk remain unknown. We will not enroll any patients who are actively breastfeeding.

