12.2 Definitions and Descriptions of Terms Used in AE Reporting

12.2.1 Adverse Event (AE)

An AE is any undesirable sign, symptom or medical condition or experience that develops or worsens in severity after starting the first dose of study treatment or any procedure specified in the protocol, even if the event is not considered to be related to the study.

Abnormal laboratory values or diagnostic test results constitute AEs only if they induce clinical signs or symptoms or require treatment or further diagnostic tests.

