12.2.7 Unexpected Adverse Event

An AE that is not consistent in nature or severity with the product information documented in the current Investigator's Brochure or package insert, or in the protocol, consent form, and/or prior reports.

Note: The following events are *not* identified as AEs in this study:

- Disease progression or relapse. However, clinical events associated with progression/relapse may be reportable as AEs.
- Medical or surgical procedures in and of themselves, including those that require hospitalization (e.g., surgery, endoscopy, biopsy procedures) are not considered AEs. However, an event or condition requiring such procedures may be an AE.
- Abnormal laboratory values will be identified and recorded As AEs only if clinical intervention is required as a result.

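### Recording only Grade 3+ and serious adverse events leaves the safety profile and the male/female toxicity summary incomplete, and two sections define a laboratory adverse event differently

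*Combined protocol and SAP*

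**What the plan says.** **Recording rule.** Section 12.1 governs what enters the case report forms, from first dose to 30 days after the end of treatment or until another anti-cancer therapy begins: "AEs of Grade 3 and above, and Serious Adverse Events (SAEs) occurring at any grade will be monitored and recorded".

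**Objectives and endpoint.** Two secondary objectives in 1.2 depend on these data: "To evaluate the safety profile of enzalutamide in MCL" (1.2.2) and "To gain preliminary data on clinical activity and toxicity of this regimen in male vs. female patients" (1.2.3). Section 10.1.2 lists adverse events by CTCAE 4.0 as a secondary endpoint and has them stratified by gender. None of these sets a lower grade limit.

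**Treatment changes.** Section 8.1 allows a hold, and then a possible reduction, for a side effect the patient cannot tolerate. Section 7.4 allows removal for other toxicity judged unacceptable. Neither attaches a grade to those grounds.

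**Laboratory values.** Section 12.2.1 says: "Abnormal laboratory values or diagnostic test results constitute AEs only if they induce clinical signs or symptoms or require treatment or further diagnostic tests". The note under 12.2.7 says: "Abnormal laboratory values will be identified and recorded As AEs only if clinical intervention is required as a result".

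**Known toxicity.** Section 3.1 gives the starting point: "As this medication has not previously been studied in patients with MCL", so adverse-effect monitoring is extrapolated from prostate cancer. Section 3.3 summarises that experience, including, in 3.3.7, "1.6% of patients treated with enzalutamide were reported to have Grade 1 or 2 hallucinations".

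**The concern.** The recording rule is narrower than the objectives and endpoint that rely on it. A non-serious Grade 1 or 2 event is an adverse event under 12.2.1 but need not appear on any form, even when it is the reason treatment was held, reduced or stopped.

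This matters more here than in a trial of a drug already characterised in the disease. The safety data cited in 3.3.1 come from prostate-cancer patients, hence men, so the documents give no tolerability data for MCL or for women. Under 5.1.2, the untreated patients who enter have few or no symptoms and would generally qualify for observation. Under 7.2, they take the drug daily until progression, intolerance, or a decision by patient or physician. For them, persistent non-severe toxicity is a large part of what a safety profile should show.

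The laboratory definitions are a second, smaller matter. They act within the grades that are recorded, so two staff members following different sections could count the same Grade 3 value differently.

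**Working it through.** The plan states no safety precision or safety sample size, so there is no figure of its own to reproduce. The calculations in Section 11.0 concern response only.

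**Inputs.** N = 20 (11.0); 6 women and 14 men expected (11.3). Enzalutamide rates from the prostate-cancer data: neutropenia 15% any grade, 1% Grade 3-4 (3.3.6); ALT elevation 10% any grade, 0.3% Grade 3-4 (3.3.6); hallucinations 1.6%, all described as Grade 1 or 2 (3.3.7).

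**Step 1: share of affected patients below Grade 3**, 1 − (Grade 3-4 rate ÷ any-grade rate).
- Neutropenia: 1 − 0.01/0.15 = 93%.
- ALT: 1 − 0.003/0.10 = 97%.
- Hallucinations: 1 − 0/0.016 = 100%.

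**Step 2: expected patients, n × p, and chance of at least one, 1 − (1 − p)^n, with n = 20.** This assumes the rates carry over to MCL.

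| Toxicity | Any grade | Grade 3-4 |
|---|---|---|
| Neutropenia | 20 × 0.15 = 3.0; 1 − 0.85^20 = 96% | 20 × 0.01 = 0.2; 1 − 0.99^20 = 18% |
| ALT elevation | 20 × 0.10 = 2.0; 1 − 0.90^20 = 88% | 20 × 0.003 = 0.06; 1 − 0.997^20 = 6% |
| Hallucinations | 20 × 0.016 = 0.32; 1 − 0.984^20 = 28% | 0 |

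**Step 3: by sex, neutropenia.** This adds the assumption that rates observed in men apply to women.
- Women: 6 × 0.15 = 0.9 at any grade, 6 × 0.01 = 0.06 at Grade 3-4. Chance of at least one: 1 − 0.85^6 = 62% against 1 − 0.99^6 = 6%.
- Men: 14 × 0.15 = 2.1 against 14 × 0.01 = 0.14.

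Sample size limits the comparison whatever is recorded. With no events, the one-sided 95% upper bound is 1 − 0.05^(1/6) = 39% for 6 women and 1 − 0.05^(1/14) = 19% for 14 men.

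**What these figures measure.** They count patients with a graded abnormality. For neutropenia and ALT they are not the number of adverse events that a lower threshold would add. A Grade 1-2 value without symptoms, treatment, further tests or intervention is not an adverse event under either laboratory rule.

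**Step 4: the two laboratory rules applied to one Grade 3 value.**

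| Consequence of the value | 12.2.1 | Note under 12.2.7 |
|---|---|---|
| Needs treatment | AE | AE |
| Prompts further tests only | AE | Not an AE |
| Causes symptoms, no intervention | AE | Not an AE |
| None of these | Not an AE | Not an AE |

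The rules disagree in the two middle rows. The second row reads a further test as something other than a clinical intervention; the protocol does not define that term.

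**The case against.** The strongest defence is that recording only severe and serious events is a reasonable choice for a 20-patient pilot of an approved drug with two large phase 3 safety datasets. Low-grade events are hard to interpret without a control arm. Section 3.3.6 reports neutropenia in 6% of placebo patients, and ALT elevation more often on placebo (18%) than on enzalutamide (10%). That is fair as a design argument, but the protocol does not make it: the objectives and endpoint remain unrestricted.

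A reader might infer that the trial cannot deliver its safety objectives at all. The documents do not support that, for four reasons.

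- Grade 3+ events and SAEs of any grade are recorded and can be tabulated by sex, and objective 1.2.3 asks only for preliminary data.
- A nearly empty safety table does not follow. Hypertension (10.6%) and falls (9%) are given without a grade split. MCL patients may also enter with neutrophils as low as 750/mm³ when the marrow is involved (5.1.6.1), so their Grade 3+ counts cannot be projected from prostate-cancer rates.
- Not all the missing information is lost for good. Blood counts, creatinine, bilirubin and AST/ALT are drawn on schedule (9.0), and 12.8 has relevant laboratory data kept. If the values are entered, they can be graded later.
- The recording threshold is not the main limit on the sex comparison; the small number of women is.

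Section 12.4 also sends the IRB some non-serious events that are unexpected, possibly related and suggest greater risk. That is a narrow reporting route and does not extend case report form capture to ordinary Grade 1-2 events.

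What survives is the mismatch for non-serious symptomatic Grade 1-2 events, which no scheduled test would recover, and the laboratory inconsistency.

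**Conclusion.** The point stands as one of incompleteness. As written, the plan yields a Grade 3+ and serious safety profile, overall and by sex, while the objectives and endpoint describe something broader. The gap is the non-serious Grade 1-2 events, including any that led to a hold, reduction or discontinuation.

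The 93%, 97% and 100% shares below Grade 3 show where the cited graded toxicity lies. They rest on prostate-cancer data; extending them to MCL and to women is an assumption, and they cover only three toxicities. The permanent loss concerns symptoms such as fatigue, hot flush, dizziness and hallucinations rather than laboratory values.

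The conflict between 12.2.1 and the note under 12.2.7 is real but narrow. It makes Grade 3+ laboratory counts depend on the section followed, and does not by itself defeat an objective. Both matters should be corrected; neither affects the primary endpoint.

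**What to change.** 1. In 12.1, record adverse events of all grades. The minimum alternative is Grade 2+, plus any grade of the events named in 3.3 (including seizure, hypertension, falls, infection, hallucinations, cytopenias, and ALT or bilirubin elevation), plus any event leading to a hold, reduction or discontinuation.
2. If the sponsor prefers the present threshold, restrict objectives 1.2.2 and 1.2.3 and the adverse-event endpoint in 10.1.2 explicitly to Grade 3+ and SAEs.
3. Enter the scheduled blood count and chemistry values and tabulate their CTCAE grades by sex, separately from the adverse-event listing.
4. Use one laboratory adverse-event definition in both 12.2.1 and the note under 12.2.7.
5. Present the male/female summary as descriptive, with intervals.

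The cost is more form entries for 20 patients. Adverse-event assessment and laboratory draws are already scheduled (9.0), so no visit or test is added. The second option costs only a wording change but gives up the low-grade information.
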